5.5.2.2 Summary of Adverse Events by System Organ Class and Preferred Term

Summaries of study-emergent AEs, AdreView™-emergent AEs, study-emergent SAEs, and AdreView™-emergent SAEs by system organ class and preferred term will be the primary presentations of the AE data. Patients will be counted only once at the system organ class level and will be counted once for each applicable preferred term; multiple occurrences of the same preferred term for a patient will be counted only once. System organ classes, and preferred terms within a system organ class, will be displayed alphabetically. In addition, summaries of common (>5% of patient in either AdreView™ or SoC group) study-emergent AEs, AdreView™-emergent AEs, study-emergent SAEs, and AdreView™-emergent SAEs by preferred term will be sorted in decreasing overall frequency.

5.5.2.3 Summary of Adverse Events by System Organ Class and Preferred Term with Respect to Event Intensity

All serious and non-serious AEs will be assessed for intensity. The intensity of all AEs will be graded as mild, moderate, or severe using the definitions:

Mild: Tolerable

Moderate: Interferes with normal activity

Severe: Incapacitating (causes inability to perform usual activity or work).

Summaries of study-emergent AEs, AdreView™-emergent AEs, study-emergent SAEs, and AdreView™-emergent SAEs by system organ class and preferred term with respect to event intensity will be provided. Patients with multiple AE/SAEs of the same system organ class or preferred term will be summarized at the maximum severity reported within that system organ class or preferred term. Patients having an AE/SAE with missing intensity will have the intensity imputed as severe. The number and percentage of patients experiencing study-

emergent AEs/SAEs or AdreView™-emergent AEs/SAEs for each system organ class and preferred term will be displayed.

5.5.2.4 Assessment of Relationship to AdreView™ or ICD Implantation

The relationship of an AE with AdreView™ will be assessed and reported by the investigator as:

- Before AdreView™ Administration
- After AdreView™ Administration - Relationship to AdreView™ is not Suspected
- After AdreView™ Administration - Relationship to AdreView™ is Suspected

The relationship of an AE with ICD implantation will be assessed and reported by the investigator as:

- Before ICD Implantation
- After ICD Implantation - Relationship to ICD Implantation is not Suspected
- After ICD Implantation - Relationship to ICD Implantation is Suspected
- Not Applicable

A suspected adverse reaction is an AE where a reasonable possibility exists for causality between AdreView™ or ICD implantation and the AE.

A summary of study-emergent AEs, AdreView™-emergent AEs, study-emergent SAEs, and AdreView™-emergent SAEs by system organ class, preferred term and relationship to AdreView™ or ICD Implantation will be provided. This table will display only those study-emergent or AdreView™-emergent AEs/SAEs that are determined to be related to AdreView™ or ICD Implantation. Patients with multiple occurrences of the same system organ class or preferred term will be summarized using the event with the strongest relationship to AdreView™ or ICD Implantation. Patients having an AE/SAE with missing relationship will have the relationship imputed as related. The number and percentage of patients experiencing study-emergent AEs/SAEs or AdreView™-emergent AEs/SAEs for each body system and preferred term will be displayed.

5.5.2.5 Summary of Adverse Events Leading to Discontinued from Study by System Organ Class and Preferred Term

Summaries of study-emergent AEs/SAEs and AdreView™-emergent AEs/SAEs leading to study discontinuation by system organ class and preferred term will be provided.

5.5.2.6 Summary of Adverse Events Leading to Death by System Organ Class and Preferred Term

Summaries of study-emergent AEs/SAEs and AdreView™-emergent AEs/SAEs leading to Death by system organ class and preferred term will be provided.

5.5.2.7 Summary of Adverse Events by System Organ Class and Preferred Term with Respect to the Treatment Given for the Event

Summaries of study-emergent AEs/SAEs and AdreView™-emergent AEs/SAEs by system organ class and preferred term with respect to the treatment given for the event will be provided.

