- f AdreView™ will be administered to all patients. First AdreView™ administration should be performed in the 15 (+7) days post-randomisation. For the low-risk cohort only, a second AdreView™ administration should be administered at 2 years (± 30 days) post-randomisation, unless patient withdraws prior to study termination or has already received an ICD. In this case the second AdreView™ scan will be offered before withdrawal becomes effective. Thyroid blocking should be performed before administration of AdreView™ in accordance with the Package Insert/Summary of Product Characteristics/IB and local regulations unless the patient has had a complete thyroidectomy.
- g At 3 hours 50 minutes after administration of AdreView™, patients will undergo a 10-minute acquisition of planar images, and whenever possible followed by SPECT acquisition, according to the imaging manual. Patients with LVEF 25% to 35% with an H/M ratio ≥ 1.6 will have a second AdreView™ scan at 2 years (± 30 days) post-randomisation.
- h Patients in the randomised AdreView™ group who are assessed as high risk, and patients in the SoC group according to the standard of care in each investigational site derived from the local implementation of internationally accepted HF guidelines. ICD implantation should be performed according to clinical practice and should be performed within 45 days after randomisation.
- i ICD interrogation does not need to be performed on the same day as the corresponding follow-up visit. ICD interrogation may be done remotely within ± 5 days of the corresponding follow-up visit.
- j AdreView™-emergent AEs are defined as any AE which occurs within 24 hours after administration of AdreView™, and in addition any AE which occurs more than 24 hours after administration of AdreView™ for which a causal relationship is assumed by the investigator.
- k Patients will be enrolled and followed up until sufficient endpoints have accrued (247 primary endpoint events). All patients will then attend an end-of-study visit within 1 month.

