5.5.2 Analysis of Adverse Events

All AEs occurring after informed consent were recorded on the eCRF. A study-emergent AE is defined as an AE that occurred after randomisation. An AdreView™-emergent AE is defined as an AE that occurred or worsened within 24 hours after administration of AdreView™ and in addition any AE which occurred more than 24 hours after administration of AdreView™ for which a causal relationship is assumed by the investigator. If the date of occurrence of an AE cannot be determined relative to date of randomisation, it will be assumed to be both study-emergent and AdreView™-emergent. AEs will be mapped to preferred terms and system organ class using the Medical Dictionary for Regulatory Activities (MedDRA) coding dictionary version 19.0.

All AEs will be listed by enrolment group and patient number, and AdreView™-emergent AEs/SAEs will be flagged.

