5.5.2.1 Overall Summary of Adverse Events

The number and percentage of patients experiencing AEs will be summarized, and p-values comparing the two study arms will be provided for the following AE categories:

- Any study-emergent AEs;
- Any serious study-emergent AEs;
- Any AdreView™-emergent AEs;
- Any serious AdreView™-emergent AEs;
- Any study-emergent AEs related to AdreView™;

- Any AdreView™-emergent AEs related to AdreView™;
- Any study-emergent AEs related to ICD implantation;
- Study-emergent AEs by maximum intensity;
- AdreView™-emergent AEs by maximum intensity;
- Any study-emergent AEs leading to discontinuation from the study;
- Any AdreView™-emergent AEs leading to discontinuation from the study;
- Any AdreView™-emergent AEs leading to death;
- Any study-emergent AEs leading to death.

In addition, number of AEs, number of study-emergent AEs, and number of AdreView™-emergent AEs will be provided.

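### SAP 5.5.2.4 imputes a missing AE relationship as related even when the patient had not yet had, or never had, the exposure in question

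*SAP*

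**What the plan says.** The rule is one sentence in SAP 5.5.2.4: "Patients having an AE/SAE with missing relationship will have the relationship imputed as related". The section covers two relationships, to AdreView and to ICD implantation, and the sentence does not say which it means.

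The same section gives investigators codes for AEs that cannot be related. The AdreView scale has "Before AdreView™ Administration". The ICD scale has "Before ICD Implantation" and "Not Applicable"; the SAP does not define the last.

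The AE window opens before either exposure. SAP 5.5.2 states: "A study-emergent AE is defined as an AE that occurred after randomisation". Table 1 in SAP 2.2 then says: "First AdreView™ administration should be performed in the 15 (+7) days post-randomisation", and its footnote h allows 45 days from randomisation for implantation. Under SAP 2.2, AdreView-arm patients with H/M of 1.6 or more get no ICD at first. The safety set in SAP 4.1.1 requires neither an injection nor an implant.

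The counts are tested. In SAP 5.5.2.1, "p-values comparing the two study arms will be provided for the following AE categories", and the list includes "Any study-emergent AEs related to ICD implantation" and the matching line for AdreView.

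SAP section 5 separately states that missing values are left missing and not replaced by estimates. It makes no exception for this rule.

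**The concern.** Imputing missing causality as related is a normal conservative convention where relatedness is possible. Here it also applies where it is not: an AE in a patient without an ICD cannot be caused by one, and an AE before the first injection cannot be caused by AdreView. Read literally, the programming would put such events in the related-AE table. That table shows only related events, so nothing would separate an imputed attribution from an investigator's.

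Small numbers could be visible. Protocol 10.2.10 puts known AdreView reactions at 1.3% for the injection site and 0.3% to 0.4% for the next most common. The planning assumptions in SAP 2.3 set device harm in AdreView-arm patients with H/M of 1.6 or more at essentially zero. What is at stake is the credibility of the ICD-related and AdreView-related lines and their between-arm p-values.

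**Working it through.** **Inputs from the documents**
- Share with H/M of 1.6 or more: 21% (LVEF 25-30%) and 25% (LVEF 30-35%), mixed 1:4; overall 24% stated (SAP 2.3).
- Planned size: 2001 randomised 1:1, so about 1000 per arm (SAP 2.3). The trial stopped early (SAP 2.4), so the counts below are rates per 1000, not forecasts.
- SoC ICD uptake, *u*: all SoC patients (SAP 2.2 design text); site standard of care (SAP 2.2, Table 1 footnote h); about half of eligible patients in practice (Protocol 4); 15% in existing practice (SAP 2.3).

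**Assumptions, not in the documents**
- *m*, the share of patients with at least one study-emergent AE whose ICD relationship is blank: 1% to 10%, equal in both arms and independent of true ICD-related AEs.
- *r*, the true ICD-related AE rate among implanted patients: 5% or 10%.
- Every high-risk AdreView patient is implanted and no low-risk one is. Blanks are in truth unrelated.

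**Step 1. Reproduce the stated share.** *s* = 0.2 × 21% + 0.8 × 25% = 24.2%, which agrees with 24%.

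**Step 2. Impossible ICD attributions per 1000.** AdreView arm: 1000 × *s* × *m*. SoC arm: 1000 × (1 − *u*) × *m*.

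| | *m* = 1% | *m* = 5% | *m* = 10% |
|---|---|---|---|
| AdreView | 2.4 | 12.1 | 24.2 |
| SoC, *u* = 100% | 0 | 0 | 0 |
| SoC, *u* = 90% | 1.0 | 5.0 | 10.0 |
| SoC, *u* = 50% | 5.0 | 25.0 | 50.0 |
| SoC, *u* = 15% | 8.5 | 42.5 | 85.0 |

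**Step 3. Which arm carries more.** The arms are equal when 1 − *u* = *s*, that is *u* = 75.8%. Above that the AdreView arm has more. At 50% uptake SoC has 500/242 = 2.1 times as many, and at 15% it has 850/242 = 3.5 times as many.

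**Step 4. Effect on the whole ICD-related line.** The rule also converts blanks in implanted patients. The reported rates are:
- AdreView: (1 − *s*)[1 − (1 − *r*)(1 − *m*)] + *sm* = *m* + (1 − *s*)*r*(1 − *m*)
- SoC: *m* + *ur*(1 − *m*)

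With *u* = 100%, *m* = 5%, *r* = 5%:
- AdreView goes from 3.79% to 8.60%, up 4.81 points.
- SoC goes from 5.00% to 9.75%, up 4.75 points.
- The difference goes from 1.21 to 1.21 × 0.95 = 1.15 points.

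With *r* = 10% the rises are 4.62 and 4.50 points, and the difference goes from 2.42 to 2.30.

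**Step 5. After restricting imputation to implanted patients.** Impossible ICD attributions fall to 0 in both arms. In the first scenario of Step 4, ignoring the short pre-implant period, the rates become 0.758 × 9.75% = 7.39% and 9.75%, a difference of 2.36 points. The remaining imputations now follow ICD uptake, so the number imputed must be visible by arm.

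**AdreView relationship.** Both arms are injected, and the gap of up to 15 + 7 = 22 days is common to both. The design gives no reason to expect impossible AdreView attributions to favour one arm.

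**The case against.** The strongest reply is that the codes already handle these cases: a completed field is never imputed, so only blanks are at issue. Protocol 11.1 asks for reasons for missing data, and Protocol 10.2.10 has both the investigator and the Sponsor/CRO assess AdreView causality for every AE, so blanks may be few. This stands as a limit on size. It does not rescue the rule, because blanks are all that the rule governs. Nor can the documents show that blanks are rare for the ICD item: the Events eCRF question described in Protocol 12.6.3.5 is a yes/no item on study drug only.

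A second reply is that worst-case handling is consistent SAP policy: missing intensity becomes severe (5.5.2.3), and an AE that cannot be dated relative to randomisation counts as both study-emergent and AdreView-emergent (5.5.2). That supports conservative imputation where the truth is unknown, but not where the exposure is known not to have occurred.

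Three stronger readings are tempting, and the documents do not support them.
- A reader might infer that the rule inflates ICD-related AEs mainly in the AdreView arm. That is not shown even for the impossible attributions, because the documents disagree on SoC uptake and later implants are allowed in low-risk AdreView patients. For the whole line, Step 4 shows nearly equal inflation even at full uptake.
- A reader might infer that imputed relatedness pulls late AEs into the AdreView-emergent class. SAP 5.5.2 requires a causal relationship assumed by the investigator, which a programmed value is not.
- A reader might set the counts against the 5% to 10% device-harm assumption in SAP 2.3. That is a different endpoint in one stratum. It is reviewed by the CEAC (SAP 3.1.3), and its analysis in SAP 5.4.3 does not invoke this rule.

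**Conclusion.** The concern holds in limited form. As written, the rule produces attributions that cannot be true: ICD-related without an ICD or before the implant, and AdreView-related before the injection. It feeds them into lines tested between arms. This is a wrong rule, not merely an unstated detail.

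Its size cannot be fixed from the documents, because the blank rate is not given. Under the assumed 1% to 10%, equal by arm, the range is that in Step 2; which arm carries more turns on whether SoC uptake is above or below about 76%. With equal blank rates the between-arm difference changes little. The consequence is confined to the relatedness safety tables and their p-values.

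The case for the change is that a related-AE count should contain no event that could not belong there. It is not that the change brings the arm difference closer to the truth: Step 5 shows it need not.

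**What to change.** Replace the sentence in SAP 5.5.2.4 with a rule applied separately to each named relationship:
- Impute a missing AdreView relationship as related only if AE onset is on or after the first AdreView injection. Otherwise assign "Before AdreView™ Administration", including for a patient never injected, since that scale has no other suitable code.
- Impute a missing ICD relationship as related only if AE onset is on or after the ICD implant. Otherwise assign "Before ICD Implantation", or "Not Applicable" if the patient was never implanted.
- Where onset relative to an exposure the patient did receive is unknown, keep the conservative imputation as related.
- Report the number of relationships imputed as related, by arm, beside each affected line.
- State that this is an exception to the no-substitution sentence in SAP section 5.

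The cost is a short SAP edit, a date check in programming and one extra count per table. Administration dates are recorded (Protocol 8.6) and ICD implantation is already summarised (SAP 5.4.3.2). The SAP is to be signed before database lock (SAP 1), so the edit belongs before that point.

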5.5.3 Analysis of Laboratory Data

Clinical laboratory parameters assessed in this study are displayed in [Table 2](#).

Table 2 Clinical Laboratory Parameters

Serum Biochemistry	Haematology
Chloride	Haematocrit
Urea nitrogen	Haemoglobin
Creatinine	Platelet count
Bicarbonate	White blood cell (WBC) count
Sodium	Lymphocyte %
Potassium	
Glucose	Troponin
Alkaline phosphatase	ST2 and Gal 3 biomarkers (if available for on-site determination).
Aspartate transaminase	
Alanine transaminase	
Bilirubin (Total)	
Brain natriuretic peptide (BNP) or N-terminal pro b-type natriuretic peptide (NT proBNP)	

Clinical laboratory tests were performed at only the screening/enrolment visit. Descriptive statistics will be displayed for the observed values by each study arm.

5.5.4 Analysis of Vital Signs

Vital sign variables are weight, BMI, systolic blood pressure, diastolic blood pressure, heart rate, respiratory rate, and pulse oximetry. [Table 3](#) presents the criteria for vital sign normal limits.

Table 3 Criteria for Normal Limits for Vital Signs

Vital Sign Parameter	Normal Limits	
	Low	High
Systolic BP (mmHg)	85	140
Diastolic BP (mmHg)	60	90
Heart Rate (bpm)	60	100
Respiration Rate (rpm)	12	22
Oxygen Saturation (%)	90	100
Body Weight (kg) ^a	41	113
Body Mass Index (kg/m ²) ^b	18.5	24.9

^a Changes in body weight are evaluated by the investigator (without taking height into account) since BMI is not collected on the eCRF.

^b BMI is calculated and analyzed retrospectively by the Sponsor, at which time height is taken into account.

Descriptive statistics will be displayed for the observed values and changes from baseline. For each vital-sign variable and each time point, the following safety endpoints will be summarized by counts and percentages:

- The occurrence of 1 or more changes from baseline, at each post-administration time point, greater than a pre-specified magnitude (i.e. 20 mm Hg for systolic blood pressure, 10 mm Hg for diastolic blood pressure, 10 beats per minute for heart rate, 10 breaths per minute for respiratory rate);
- The occurrence of post-administration values outside the normal limits (Table 3). Shift tables based on the normal range will be prepared.

5.5.5 Analysis of ECG Parameters

A standard 12-lead ECG was performed at only the Screening/Enrolment visit. Table 4 presents the criteria for ECG normal limits.

Table 4 Criteria for Normal Limits for ECGs

ECG Variable	Normal Limits (ms)	
	Low	High
PR interval	120	200
QRS interval	50	100
RR interval	600	1000
QT interval (gender not specified)	-	≤440
QTc interval ^a (gender not specified)	-	≤440

^a No lower boundary set for QTc.

The QT interval will be corrected using Fridericia's formula and Bazett's formula as follows:

- Fridericia's formula: $QTcF = QT/RR^{1/3}$
- Bazett's formula: $QTcB = QT/RR^{1/2}$

Descriptive statistics will be displayed for the observed values by each enrolment group and p-values of the comparison between SoC and AdreView™ group will be presented by using two sample t-test. The occurrence of observed values outside the normal limits will be summarized by counts and percentages.

Overall investigator interpretation of ECG will be categorized as normal, abnormal (Not Clinically Significant) and abnormal (Clinically Significant) and will be summarized by counts and percentages.

5.5.6 Analysis of Physical Examinations

The results of the physical examinations at baseline (complete physical examinations) and at each post-randomisation time point (brief physical examinations) will be summarized.

6 SPECIAL STATISTICAL TOPICS

This study was discontinued prematurely by the sponsor. Due to the early termination of the study, the following objectives for the study will not be performed and will be evaluated in the future if needed.

- The healthcare resource utilization data including ICD implantation, all hospitalizations, treatment of AEs, and AdreView™ administration
- Statistical relationship between AdreView™ global and/or regional distribution quantified on Single Photon Emission Computed Tomography (SPECT) images with the same clinical outcomes as with planar H/M ratio

